Sequences will be processed with the UPARSE pipeline as implemented in USEARCH v 8.0.1623.⁴⁶ Details for each processing step are outlined. For quality filtering the forward and reverse 16S PCR primers along with any sequencing adapter will be trimmed off the raw reads using cutadapt v1.8. Following this the forward and reverse reads will be overlapped to reconstruct the full amplicon. This will be done using the fastq_mergepairs option in USEARCH v 8.0.1623. Following this the reads will be quality filtered using the maximum expected error method and then truncated at a length of 173 base pairs. Sequences will be dereplicated, where identical reads are merged and counts of these reads are retained, with vsearch v1.1.3

hosted on GitHub (“<https://github.com/torognes/vsearch>”). Singleton reads will be filtered out with vsearch prior to clustering. The remaining sequences are then clustered into groups of 97% identity, designated as Operational Taxonomic Units (OTUs) with the cluster_otus command in USEARCH v 8.0.1623. To construct an OTU table the filtered reads, with singletons included, were searched against the clustered OTU sequences with usearch_global in USEARCH v 8.0.1623.

Taxonomy will be assigned to each of the representative sequences using the RDP Naïve Bayesian Classifier v 2.2⁴⁷ as implemented in Qiime 1.9.0⁴⁸ using the most recent version of the Greengenes database⁴⁹. The RDP classifier uses a bootstrap procedure to assign confidence values to the taxonomic assignments at each level of the taxonomy. The OTU sequences will be aligned with PyNAST, a flexible tool for aligning sequences to a template alignment⁵⁰. Gaps in the alignment will be removed using Qiime’s ‘filter_alignment.py’, and a phylogeny constructed using FastTree, a tool for inferring phylogenies for alignments with up to hundreds of thousands of sequences⁵¹, using default parameters. All remaining analysis will be done in R, a programming language and software environment for [statistical computing](#) and graphics (R Core Team, 2015) using functions from phyloseq⁵² DESeq2⁵³ and vegan.

The diversity within each sample, also known as α diversity, will be measured using the Shannon index. This is a measure of both the organismal richness of a sample and the evenness of the organisms' abundance distribution⁵⁴. A two-sided Mann-Whitney test (with False Discovery Rate multiple test correction) will be used to determine if there were significant differences in Shannon diversity between cases and controls.

Diversity between samples (β -diversity) will be evaluated using weighted UniFrac, a rank-based ordination method and visualized with Non-metric Multidimensional Scaling (NMDS). β -diversity represents the explicit comparison of microbial (or other) communities based on their composition or relative abundance. β diversity metrics thus assess the differences between microbial communities. To test whether there are significant differences in community structure between groups the UniFrac distance matrix will be tested with permutational multivariate ANOVA (PERMANOVA) implemented in the adonis function in the vegan R package. Differential abundance of individual OTUs between groups will be assessed using generalized linear models with a negative binomial distribution as is used commonly for RNA-seq⁵³. The similarity in data structure between RNA-seq and 16S allow us to adapt already mature methods⁵⁵. This analysis will be performed in DESeq2 v1.8.1 using default parameters.

5. Why you/your group should do it (relevant prior experience and skills, collaborators for technical gaps, preliminary data showing feasibility):

[name] has a lifelong interest and expertise as well as publications in neonatal GI pathophysiology and NEC.

[name] has completed a year of supplementary training in the study of the neonatal intestinal tract in Philadelphia. He is also skilled in study design and statistical analysis and has a Master degree in Epidemiology.

The collaborators include [name], the director of the ACHRI Genomics facility, [name] is a research scientist at -University of Calgary and an expertise in microbiome, [name] (neonatologist and epidemiologist), and [name] – Pediatric Pharmacists.

6. Plans for dissemination or translation of results and plans for next steps in study of topic: The microbiome data will constitute a comprehensive clinical and biological study of probiotic administration in this population. Results will be presented at national and international meetings and submitted for publication.

Do probiotics modulate the intestinal microbiome in extremely premature infants? Statistical Analysis Plan

Principle Investigator: [name]

REB16-0542

October 11, 2017

Characteristics variables will be analyzed using independent 2-sample t tests when continuous and Pearson χ^2 test when categorical. A P-value of less than 0.05 will be considered significant.

For the microbiome, the diversity within each sample, also known as α diversity, will be measured using the Shannon index. This is a measure of both the organismal richness of a sample and the evenness of the organisms' abundance distribution. A two-sided Mann-Whitney test (with False Discovery Rate multiple test correction) will be used to determine if there were significant differences in Shannon diversity between cases and controls.

Diversity between samples (β -diversity) will be evaluated using weighted UniFrac, a rank-based ordination method and visualized with Non-metric Multidimensional Scaling (NMDS). β -diversity represents the explicit comparison of microbial (or other) communities based on their composition or relative abundance. β diversity metrics thus assess the differences between microbial communities. To test whether there are significant differences in community structure between groups the UniFrac distance matrix will be tested with permutational multivariate ANOVA (PERMANOVA) implemented in the `adonis` function in the `vegan` R package. Differential abundance of individual OTUs between groups will be assessed using generalized linear models with a negative binomial distribution as is used commonly for RNA-seq. The similarity in data structure between RNA-seq and 16S allow us to adapt already mature methods. This analysis will be performed in DESeq2 v1.8.1 using default parameters.

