4.3 Sample Size and feasibility

A total of 100 infants of birth weight <1000g are born annually and admitted to FMC NICU.

Assuming that 80% of parents' consent to their infant's participation in the study, it will be feasible to complete enrollment of 60 babies in the first year of the study. This study will randomize 30 infants to be given probiotics and 30 infants be in the control group where no probiotic given. The 2 groups will be matched by gender, gestational age +/- one week, birth weight +/- 100g, SGA vs AGA/LGA status and type of delivery.

A sample size of 30 infants per group will allow for a power of 0.8 and an alpha of 0.05 for a two-tailed Wilcoxon-Mann-Whitney test to detect a 0.7 effect size when comparing relative abundance of stool probiotic microbial species in the group given Florababy versus the one given placebo, conservatively assuming a background logistic distribution (G-Power 3.1 software).

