4.4 Variables collected

- a) Demographic variables: Gestational age, birth weight, head circumference at birth, gender, mode of delivery, singleton/multiple and rank, maternal administration of corticosteroids and antibiotics.
- b) Clinical variables: Apgar scores, umbilical cord pH and base excess, first patient blood gas pH and lactate, day of life at start of feeds and at start of study, total days of study drug, antibiotic use during NICU, use of inotropes and vasoactive substances, steroids and medical and/or surgical treatment for PDA, type of feeds during NICU and at discharge.

- c) Outcome variables: mortality; total days of TPN, total days NPO and number of separate NPO events; age, head circumference and weight at discharge home; diagnosis of: feeding intolerance, time taken to reach full enteral feeds (at least 150ml/kg/day), suspected NEC, NEC, cow milk protein allergy, late onset sepsis, BPD, ROP.

4.5 Study protocol.

Infants will be identified within 24 hours of birth and parents will be approached for informed consent.

Once consent is obtained, subjects will be randomly assigned in blocks of 4 to receive either Florababy probiotics orno. Investigators will conduct the randomization using a computer-generated table of random numbers generated at the University of Calgary.

Preparation and Administration of Study Drug

The study probiotic will be started after the first stool sample is obtained and after informed parental consent. Very small amounts of breast milk/colostrum (0.1ml to 0.2ml every 4 hours) are usually given to all premature babies within the first 48 hours of life. Actual feeds of breast and/or human milk (donor milk) are initiated from 72 hours onwards (starting at 10ml/kg/day and increasing slowly thereafter). The study probiotic (at a dose of 0.5g per day) will be started at or after 72 hours of life. It will be administered in 1 ml of sterile water prior to a feed.. No drug will be given to infants in the control group. If the infant is placed NPO, the study drug will be stopped and restarted together with refeeding.

The study probiotic will be given until 34 weeks corrected gestational age.

Sample collection

Nurses will collect the stool samples at 4 time points: prior to, two weeks and four weeks after probiotic administration is commenced, and one week after it is stopped. Stool samples for the control group will be done at a matched feeding and gestational age time points.

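### The Mann-Whitney test that sizes the trial is absent from the analysis text, and the only Mann-Whitney test there carries an FDR correction with no stated family or level and no separate place for the week-4 primary stool

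*SAP*

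**What the plan says.** **Sizing (Protocol section 4.3).** Thirty infants per group are said to give "a power of 0.8 and an alpha of 0.05 for a two-tailed Wilcoxon-Mann-Whitney test" and "to detect a 0.7 effect size when comparing relative abundance of stool probiotic microbial species", with a logistic parent distribution. No allowance for multiple testing is mentioned.

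**Outcomes (Protocol section 1).** The primary outcome is a difference in stool microbiome after four weeks; no metric is named. The stool microbiome one week after stopping is a secondary outcome. Week 2 is not listed as an outcome.

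**Sampling (Protocol section 4.5, Sample collection).** "Nurses will collect the stool samples at 4 time points": before the start, two and four weeks after it, and one week after stopping.

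**Analysis (Protocol section 4.6, Bioinformatic analysis, and the SAP, in the same words).** Three analyses are listed and none is called primary:
- Shannon diversity: "A two-sided Mann-Whitney test (with False Discovery Rate multiple test correction) will be used to determine if there were significant differences in Shannon diversity".
- Community structure: "the UniFrac distance matrix will be tested with permutational multivariate ANOVA (PERMANOVA"), with no multiplicity rule.
- Abundance of individual OTUs: negative binomial models in DESeq2.

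Neither document says which tests form the FDR family, how many there are, at what level they are controlled, or whether week 4 is among them. The SAP's 0.05 threshold stands in its paragraph on characteristics variables, and the text does not say whether it extends to FDR-adjusted p-values.

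**The concern.** The alpha and test behind the sample size are not those of any test in the analysis text. The sized variable has lost its Mann-Whitney test. The variable that has a Mann-Whitney test has a correction that the sizing did not consider.

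An FDR correction does something only over two or more tests. If the family is the stool times, the one time that the protocol singles out as primary is corrected together with times of lower rank. That could include the pre-dose stool, where randomisation makes any group difference a chance one. The primary comparison would lose power with nothing gained for the primary question.

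Because the family is not stated, it could also be chosen after the data are seen. A single week-4 p-value could then be reported as significant or not, depending on that choice.

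**Working it through.** **1. Reproduce the stated power.** Inputs from Protocol section 4.3: n = 30 per group, d = 0.7, two-sided alpha 0.05, logistic parent. The asymptotic relative efficiency of the Mann-Whitney test against the t test for a logistic parent is π²/9 = 1.097.
- Effective n per group = 30 × 1.097 = 32.9
- Degrees of freedom = 2 × 32.9 − 2 = 63.8
- Noncentrality = 0.7 × √(32.9/2) = 2.84
- Power from the noncentral t = 0.7985

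The stated 0.80 is reproduced, and only with the full alpha of 0.05.

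**2. Compare the sized test with the planned tests.**

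| | Variable | Test | Correction |
|---|---|---|---|
| Sizing (4.3) | relative abundance of probiotic species | Mann-Whitney | none |
| Analysis (4.6, SAP) | Shannon diversity | Mann-Whitney | FDR, family not stated |
| Analysis (4.6, SAP) | weighted UniFrac distances | PERMANOVA | none stated |
| Analysis (4.6, SAP) | individual OTUs | DESeq2 | default parameters |

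No analysis row matches the sizing row.

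**3. Infer the FDR family.** The plan gives one index (Shannon) and one contrast (cases against controls). The multiplicity left in the design is stool time. Possible families are two stools (week 4 and post-stop, the times named as outcomes), three (all stools after the start) or four (adding the pre-dose stool). The documents choose none of these.

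**4. What the choice does to one result.** Benjamini-Hochberg (BH) compares the i-th smallest of m p-values with 0.05 × i/m. Take a week-4 p of 0.02, with every other p at 0.08 or more. The adjusted week-4 value is m × 0.02:
- m = 1: 0.02, significant
- m = 2: 0.04, significant
- m = 3: 0.06, not significant
- m = 4: 0.08, not significant

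**5. Worst-case power by formula.** When no other stool differs, BH is close to testing at 0.05/m. With the method of step 1, power is 0.706 for m = 2, 0.6485 for m = 3 and 0.607 for m = 4. These are Bonferroni values and close to a floor for BH.

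**6. BH by simulation at the same design point.** Assumptions: logistic data with SD 1, a shift of 0.7 where a stool differs, within-infant correlation between stools of 0 or 0.5, BH at 0.05, and 20,000 trials per row. Uncorrected power in the same simulations is 0.778-0.788.

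| Family | Stools that differ | Week-4 power, correlation 0 | Correlation 0.5 |
|---|---|---|---|
| 2 | week 4 only | 0.689 | 0.688 |
| 2 | both | 0.760 | 0.753 |
| 3 | week 4 only | 0.631 | 0.633 |
| 3 | week 4 and one other | 0.711 | 0.699 |
| 3 | all three | 0.753 | 0.747 |
| 4 | week 4 only | 0.589 | 0.585 |
| 4 | week 4 and one other | 0.658 | 0.649 |
| 4 | week 4 and two others | 0.710 | 0.699 |

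The range is about 0.58 to 0.76. If the pre-dose stool is in the family, that member is null and the best case is about 0.70-0.71.

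**The case against.** The strongest reply is that the power of 0.80 and the FDR clause belong to different variables. The sizing concerns relative abundance, and no FDR wording is attached to that anywhere. If section 4.3 describes the primary test, that test loses nothing. For Shannon no effect size is given, so its power is unknown. A reader might infer that the trial's power has dropped from 0.80 to some 0.6-0.7. The documents do not support this: it carries an effect size from one variable to another and treats an inferred family as stated. It also leaves out the favourable cases, where every stool in a family of two or three differs and the loss is only about 2 to 4 points.

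A reader might also infer that PERMANOVA is run uncorrected at all four stools, with a false-positive chance of about 1 − 0.95⁴ = 0.185 if the tests were independent. The text says only that groups are compared. It does not say at which stools, and no section plans a pre-dose test.

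A third reply is that freeing week 4 from the FDR family is not enough. With no primary metric named, Shannon and PERMANOVA would each be tested at 0.05 at week 4, giving up to 1 − 0.95² = 0.0975 if independent.

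The first two replies limit what can be claimed about size, and the third changes the remedy. None of them supplies the missing test, the missing family, or the separation of the week-4 stool.

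**Conclusion.** The concern holds as a mismatch between sizing and analysis that should be corrected. Four things can be read directly from the documents: the sizing uses an unadjusted 0.05; the sized test is missing from the analysis text; the only Mann-Whitney test there is FDR-corrected with no family or level; and the week-4 stool has no separate status in the tests.

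The power cost is an illustration. It assumes a family made of two to four stool times, BH at 0.05, and d = 0.7 with a logistic parent wherever a stool differs. Under those assumptions simulated week-4 power goes from about 0.78 to about 0.58-0.76. If week 4 stands alone, nothing is lost. The power of the Shannon comparison cannot be worked out from the documents.

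**What to change.** In Protocol section 4.6 and the SAP:

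1. Name one primary week-4 variable and one test. To match section 4.3, this is the two-sided Mann-Whitney test on relative abundance of the probiotic species. Define the variable as one number per infant, since the product has five strains. Test it alone at 0.05, outside any FDR family.
2. Put the remaining comparisons (Shannon and PERMANOVA at week 4, and the week-2 and post-stop comparisons) in a stated FDR family, with the level given and the same rule for both methods. Say how the per-OTU DESeq2 results stand in relation to it.
3. Describe the pre-dose stool by group without a test.

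If the primary test is to stay inside an FDR family, section 4.3 should say that its 0.80 does not allow for the correction, and give the power for the stated family. The Bonferroni values in step 5 should not be entered there as FDR power. On that worst case, 0.80 would need 37, 41 or 43 infants per group for two, three or four tests.

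The recommended change costs a few sentences and no infants, samples or data. Its downside is that the secondary tests, PERMANOVA included, become somewhat stricter.

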Furthermore, the intestinal microbiomes of infants admitted to NICUs have different patterns compared to infants not admitted to NICUs. This is due to exposure to a different environment in NICUs, and the use of antibiotics and sterile formulas. There is even less data about the establishment of the microbiome in very preterm infants, how that evolves with time, what constitutes a “good” profile and how it correlates with intestinal or systemic pathology. What we know shows that the microbiome in preterm infants demonstrates decreased diversity, altered species proportions and even different behavior of the same species when compared with the term infant (15-17).

2.2 Microbiome and intestinal disease in the neonate.

The microbiome plays an essential role in nutrition, mucosal immunity, and GI epithelial integrity. Current evidence suggests that interactions between the altered microbiome and the intestinal epithelium play an important role in the development of feeding intolerance, allergy, sepsis and necrotizing enterocolitis (NEC) (18-20).

NEC is a multifactorial disease and one of the major pathologies affecting preterm infants. It is associated with significant mortality and morbidity, including long term neurologic disability. Systematic interventions to predict and prevent NEC have generally remained elusive. Feeding breastmilk and colostrum to preterm infants is helpful and use of probiotics has shown good results in a number of studies, though significant concerns remain. Concerns include: the limited safety data for infants born < 1000g and a domestically available probiotic formulation with demonstrated efficacy, safety, and regulatory approval. There remain concerns that the regulatory framework for approval of probiotics does not approach the rigor for drugs (21-22). Systematic reviews of randomized controlled trials concluded that probiotics as a group significantly reduce the incidence of severe NEC (23). The principle and methodology of such generalizations is controversial (24-26). Better tools are needed to aid in the understanding and monitoring of probiotic administration.

The technology available to define the intestinal microbiome has been a sizable obstacle. The vast majority of species cannot be cultured and the genomic technologies have just only very recently reached a level where the ratio of cost and resolution allows for reasonably efficient research use.

2.3 Techniques to study gut microbiota and microbiome.

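### Default DESeq2 size factors use only OTUs found in every stool, so on a sparse table the analysis may stop or silently rest on one to three OTUs

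*SAP*

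**What the plan says.** The last paragraph of the SAP, repeated in the protocol (section 4.6, Bioinformatic analysis), sets the model: "Differential abundance of individual OTUs between groups will be assessed using generalized linear models with a negative binomial distribution". It then fixes the settings: "This analysis will be performed in DESeq2 v1.8.1 using default parameters". The justification for borrowing an RNA-seq method is one sentence: "The similarity in data structure between RNA-seq and 16S allow us to adapt already mature methods".

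Neither document names a size-factor method, a rule for zeros or a filter on rare OTUs. In protocol section 4.6, singleton reads are removed before clustering and then restored: "To construct an OTU table the filtered reads, with singletons included, were searched against the clustered OTU sequences". The only statement bearing on sparsity is qualitative, at the end of protocol section 2.1: "the microbiome in preterm infants demonstrates decreased diversity, altered species proportions".

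The design gives two arms of 30 (section 4.3: "This study will randomize 30 infants to be given probiotics and 30 infants be in the control group") and repeated stools (section 4.5: "Nurses will collect the stool samples at 4 time points"). That makes 60 stools per time point and up to 60 × 4 = 240 in all. The plan does not say whether DESeq2 is run on 60 stools or on the pooled table.

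**The concern.** Size factors put samples of different sequencing depth on one scale, and every OTU's fold change is read on that scale. Taking all defaults means accepting median-of-ratios size factors, which exclude any OTU with a zero count in any sample. RNA-seq tables usually keep many features after that exclusion; a preterm stool table may not.

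Two things can go wrong. If no OTU is universal, the default stops, and someone must choose another normalisation after seeing the data. If one to three are universal, the run completes without warning, and those few OTUs set the scale for the whole table. A change in them then appears as an opposite change in everything else.

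At stake is the SAP's only test of which individual OTUs differ between the arms.

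**Working it through.** **The plan's own figure.** The DESeq2 step has none. The only design figure is 30 per group for power 0.8 (section 4.3: two-tailed Wilcoxon-Mann-Whitney, effect size 0.7, logistic parent). With asymptotic relative efficiency π²/9 = 1.097 and a noncentral t, power at 30 per group is 0.7985, so it reproduces. It does not involve size factors.

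**Step 1: which OTUs enter the default size factor.** An OTU of prevalence p, independent between samples, is non-zero in all N samples with probability p^N.
- N = 60: 0.90^60 = 0.0018; 0.95^60 = 0.046; 0.99^60 = 0.547.
- N = 240: 0.99^240 = 0.090.

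Only near-universal OTUs count, and pooling time points makes this stricter.

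**Step 2: how many there would be.** The documents give no prevalence, so I assume 150 OTUs, 60 stools and Beta-distributed prevalence. With q the mean of p^60, the number of universal OTUs is Binomial(150, q). For Beta(a, 1), q = a/(a + 60).

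| Assumed curve | Mean prevalence | Expected number, 150q | None | One to three |
|---|---|---|---|---|
| Beta(0.5, 1.5) | 0.25 | about 0.18 | 84% | 16% |
| Beta(1, 1) | 0.50 | 150/61 = 2.5 | 8% | 68% |
| Beta(2, 1) | 0.67 | 300/62 = 4.8 | under 1% | 28% |
| Beta(4, 1) | 0.80 | 600/64 = 9.4 | about 0% | about 1% |

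(A simulation gave 69% for the 68% entry.) A different curve with mean 0.80, Beta(2, 0.5), gives about 25 universal OTUs. The silent failure therefore sits in a middle band. At the sparse end the failure is visible, and at the dense end it largely disappears.

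**Step 3: common shift by chance.** Assume a within-group log-SD of 1.5 and 30 stools per arm. With one reference OTU, the between-arm difference in mean log size factor has SD 1.5 × √(2/30) / ln 2 = 0.56 log2 units. With two it is 0.56/√2 = 0.40. With three, simulation gives about 0.37. All other OTUs share the shift.

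**Step 4: common shift from a true change.** If every reference OTU changes by a factor f, all size factors in that arm scale by f, and every other log2 fold change moves by −log2(f). Halving gives +1.0 and doubling gives −1.0. With exactly one reference OTU, its own normalised count is the same in every sample, so its estimated fold change is zero whatever the truth.

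A simulation of median-of-ratios size factors (30 v 30 stools, 150 unchanged OTUs at 25% prevalence, log-SD 1.2) had a majority of the universal OTUs double. The median shift in the unchanged OTUs was −1.00 with one universal OTU, −0.98 with two, −0.64 with three (two doubled) and −0.58 with five (three doubled). The full opposite shift thus needs all the references to change together.

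**Step 5: the alternative.** In the same simulation, with no change, a doubling or a quadrupling, size factors from positive-count geometric means gave mean shifts between −0.11 and +0.01, with SD about 0.15.

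**The case against.** The strongest reply is that sparsity is assumed. Low diversity within a stool is not low prevalence across infants: a few taxa shared by every infant would also be low diversity. Deep sequencing and restored singletons push towards fewer zeros. This stands, and it is why the point is conditional.

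Second, the chance shift is not shown to create false findings. The same noise enters each OTU's residual variance. In a two-group t test on reference-normalised log abundance, null rejection was 4.9% with one reference and 4.4% with three. An unshrunken negative binomial Wald test (not DESeq2 itself) rejected 34–36% of nulls, but already 25–30% with perfect normalisation. So the noise alone is the weaker part of the case. A true change in the reference OTUs is a bias, and this argument does not remove it.

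Third, other analyses do not use these size factors. They include the qPCR in section 4.6 and the comparison of probiotic-species abundance that section 4.3 is powered on. A reader might infer that DESeq2 is the trial's only route to organism-level conclusions; the protocol does not support that. The cover is partial, though: the qPCR targets include neither of the product's genera, and the section 4.3 comparison does not appear in the SAP.

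Finally, a competent analyst would notice an error and work round it. But that is an unplanned choice, and the silent case gives no signal.

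**Conclusion.** The point holds as a conditional weakness in a stated rule. Depending on sparsity that the documents do not report, the rule may stop with an error, rest silently on one to three OTUs, or work acceptably. The percentages rest on the assumed Beta curves, 150 OTUs, 60 stools and independence. The chance SD of about 0.4 to 0.6 rests on the assumed log-SD of 1.5.

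A reader might infer that the OTU results will be biased, or that a one-log2 shift is to be expected. The documents support neither. The ±1.0 follows by construction once the reference OTUs are assumed to halve or double, and nothing in the protocol says that universal OTUs would be displaced. Shannon diversity, UniFrac/PERMANOVA, the qPCR and the sample size are untouched. It should be fixed because the remedy is nearly free, not because harm is certain.

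**What to change.** In the SAP and in protocol section 4.6, keep the package and version, and replace the blanket reference to defaults with wording such as:

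*Default settings will be used except that size factors are estimated from geometric means of positive counts only. The number of OTUs determining the size factors will be reported. Results under the default size factors, where computable, will be given as a sensitivity analysis.*

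Write out the formula, including whether the divisor is the number of samples or of positive samples. The cost is a couple of lines of code and slightly more analysis work.

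A prevalence filter is no substitute: OTUs with any zero already contribute nothing to the default size factors, so removing the rarest leaves those factors unchanged.
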